	The evaluation of the primary and secondary effectiveness endpoint(s) will be performed both in the PPS and in the FAS for the initial treatment phase, and only for the FAS for the repeat phase.
	• For the primary effectiveness endpoint, the PPS and the FAS will be both considered equally important for the primary analysis. The analysis of the primary effectiveness endpoint will be performed on the PPS (primarily) and FAS. Confirmatory testing will be performed in a hierarchical ordering. Non-inferiority is demonstrated only if the results are consistent for both analysis populations.
	Subjects with missing baseline MVDS score and / or missing MVDS score at Week 24 after last injection of the initial treatment phase will be considered as non-responders for the primary analysis on the FAS. To calculate the primary outcome measure, the improvement over Baseline in the MVDS score assessed live by the blinded evaluator at the site at Week 24 after last injection of the initial treatment phase by subtracting the Midface Scale grade obtained at Baseline. The proportion of subjects with MVDS score improvement of ≥1 point will be then calculated for each treatment group.
	
 
The primary effectiveness endpoint will be evaluated by means of a one-sided two-group Farrington-Manning test of proportions with the following hypotheses:
 
H0: pA – pB ≤ d0
 
H1: pA – pB > d0.
 

	At this, pA is the response rate for saypha® VOLUME Lidocaine and pB is the response rate for this difference means that the response rate of saypha® VOLUME Lidocaine is lower than the response rate for

The non-inferiority margin is -10%. The study decision will be based on a Farrington-Manning-statistics with a one-sided type I error rate level of 0.025.
Sensitivity analyses of the primary effectiveness endpoint will be performed on the FAS addressing the different reasons for non- adherence and covering the following aspects to underline the robustness of the results:

 
Complete case analysis: In this analysis only those subjects will be included for whom the primary endpoint could be calculated;
 

 
Subjects with non-allowed concomitant medication / treatments before Week 24 after last injection of the initial treatment phase may be regarded as non-responder.
 

 
Multiple imputation under MNAR assumption for imputing missing MVDS scores at Week 24 assessed live by the blinded evaluator.
 

• All secondary effectiveness endpoints will be analyzed in an exploratory manner by means of descriptive statistics.
The descriptive tables will show the statistics by time of assessments as well as for the changes from baseline (if applicable). Concerning the follow-up for initial treatment, the last measurements / assessments before first treatment are defined as baseline. Concerning the time after repeat-treatment, the measurements / assessments at Visit RT1 before first repeat-treatment are defined as baseline.
Safety analyses
Safety analyses will be based on the SAF.

 
Incidence of AEs will be summarized by Preferred Term and System Organ Class, and also by intensity (severity), causal relationship to the respective device or procedure, and seriousness.
 
The frequency and occurrence rate, maximum intensity, overall duration, and seriousness of injection site reactions within four weeks (28 days) after baseline treatment, after repeat-treatment injection, respectively, and 6 weeks in case of touch-up treatment will be
 

summarized by device.
Analysis of subgroups The primary analysis will be based on the total trial population. Besides the total study population, the following subgroups will be analyzed by descriptive statistical methods for the primary and the main secondary effectiveness endpoints:

 
Injection equipment: Needle versus cannula
 
Gender: Female versus male
 
Fitzpatrick skin type
 
Race and ethnicity
 
Age group
 

In addition, incidence of AEs and injection site reactions in will be summarized by preferred term (PT) and system organ class (SOC) within all of the above-mentioned subgroups. Frequency and occurrence rate injection site reactions will be summarized within all of the above-mentioned subgroups.

Interim analysis (IA)
An interim analysis (IA) assessing the safety and effectiveness will be
performed after all subjects have completed the follow-up visit 48 weeks
after their last injection during the initial treatment phase (Visit 9 (SV1)).

A schedule of assessments for initial treatment phase is given in Table 1 (Visit 1 to Visit 9 (SV1)) for the screening phase for repeat-treatment (SV2 to SV4) in Table 2, and for optional repeat-treatment phase in Table 3 (Visit RT1 to Visit RT5).

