	In order to evaluate any potential vision changes, visual examinations (including Snellen visual acuity, confrontational visual fields and ocular motility) will be additionally performed at treatment visits (prior to- and 30 min after any treatment) and at all follow-up visits of the initial and repeat-treatment phase. A basic neurological examination (F.A.S.T) will be performed for all subjects who show signs of ophthalmic complications due to filler injection.	
	Abnormal clinically significant changes in visual examination or experience neurological symptoms indicative of a vaso-occlusional event after any treatment will lead to withdrawal of the subject from further treatment(s) in case an eye specialist or neurologist confirm that the result is related to a vascular injection of the dermal filler. The subjects may remain in the study for at least safety assessments during the scheduled study visits. Pre-defined activities following a related vaso-occlusional event will be performed.	
SUBJECT SELECTION	N AND ELIGIBILTY CRITERIA	
Number of investigation sites	Subjects will be recruited by approximately 16 investigation sites located in the USA	
Number of subjects	Approximately 486 subjects in total will be randomized and treated resulting in 437 evaluable subjects for the primary endpoint.	
	Randomization will be in a 2:1 ratio (test device: 324, comparator device: 162). Approximately 300 subjects are estimated to qualify for repeat treatment.	
Eligibility criteria – Baseline treatment		
Inclusion criteria (baseline treatment)	A subject must meet ALL of the following criteria to be ELIGIBLE for this clinical investigation:	
	
 
Male or female subjects aged 22 – 75 years (inclusive) of age at Screening
 
	
	
 
Subjects with bilateral, approximately symmetric moderate to severe midface volume deficit (severity scores of 2 or 3 on the 5-point Midface Volume Deficit Severity Scale), as assessed by the blinded evaluator at
 
	

	the site
	3. Females of childbearing potential must have a negative urine pregnancy test and must agree to use an effective method of birth control throughout the entire study
	Male subjects with female partners of child-bearing potential must agree to use contraception throughout the entire study (surgical sterilization or a physical barrier such as a condom).
	
 
Healthy skin in the midface area and free of diseases that could interfere in cutaneous aging evaluation
 

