11	Visual exams (including Snellen visual acuity, confrontational visual fields and ocular motility). The subject should wear the same corrective eyewear (i.e., glasses/contact lenses) at each assessment, if appropriate. At treatment visits: Examination will be performed both before and 30 min after the injection. For subjects not receiving TUP, exams will only be performed once.
12	Volumetric change measurement on photographs will be done centrally by the photography provider once the photography images are received at the photography provider after all subjects have finalized Visit 9 (SV1). The left and right midface will be evaluated separately.
13	Concerning only subjects who receive touch-up treatment
14	All subjects must be asked if they are experiencing or have experienced any signs/symptoms of vision changes or stroke since the injection or other events indicating an embolic event.
15	Repeat-treatment is optional and possible for all subjects who fulfill the eligibility criteria, irrespective of the treatment (either test device or comparator device) they received in the initial treatment (baseline plus touch-up). The subject does NOT have to return to his/her baseline severity to be permitted to receive a repeat-treatment, but the present condition of midface volume deficit has to meet the initial inclusion level of severity scores of 2 or 3 on the 5-point MVDSS (see section 6.3.5). The score does not have to be the same on both sides but must be 2 or 3. In case the subject is eligible in MVDSS score at Visit 9 (SV1), a full eligibility assessment for repeat-treatment will be performed (see Table 3).
16	Touch-up treatment for optimal correction if deemed necessary in the discretion of treating investigator
17	A basic neurological examination (F.A.S.T) will be performed for all subjects who show signs of ophthalmic complications due to filler injection in visual exams

18	Evaluation and grading of nasolabial folds severity by the blinded evaluator at the site (live assessment) using the 5-point NLF-SRS
19	Explain diary use incl. documentation of injection site reactions / symptoms of interest to the subject.

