# 6.5.3 Visit 2a - Telephone Visit (24 to 48 hours (±4 hours) after baseline treatment)

**Note:** The time of the telephone call has to be documented; it has to be conducted 24 to 48 hours ( $\pm$ 4 hours) after the end of injection at Visit 2 (see section 6.4.9)

- Ask for any changes in AEs and new AEs (see section 14) including AESIs (see section 14.1)
   In case of an AE including vision changes, neurological issues, or an unbearable injection site reaction an unscheduled on-site visit must be performed (see section 6.5.17)
- Ask for changes in concomitant treatments (see section 6.4.7)
- Remind the subject to document injection site reactions / symptoms of interest in the diary (see section 6.4.19)

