## 14.2 Method of detecting AEs

AEs will be detected by observation and by asking the subject about the occurrence of AEs. Care should be taken not to introduce bias when eliciting AE information from the subject. Open-ended and non-leading verbal questioning is the preferred method and appropriate questions include:

- *"How are you feeling?"*
- "Have you had any medical problems since your last visit/contact?"
- "Have you taken any new medication since your last visit/contact?"

In order to identify potential AEs post-administration of device safety evaluation 15 minutes after the device administration needs to take place (see section 6.4.20).

All SOI(s) documented by the subject in the eDiary (see section 6.4.19) must be verified by the investigator either by specific questioning of the subject and/or physical examination or visual inspection. SOI(s) *considered clinically significant* should be documented as AE(SI)(s). SOIs that turn out to be not clinically significant (see section 20.5.1 for examples) due to any reason are not considered as AE(SI) and need not to be documented as AE(SI) in the eCRF. However, the investigator should add a statement in the subject's source records why the SOI was not considered clinically significant, i.e., as AE(SI).

All AESIs (serious and non-serious, see section 14.1 for definition) and any other embolic event (regardless of seriousness and / or relationship to device or procedure) resulting from SOI assessment have to be reported by the investigator to the sponsor's representative within 24 hours of awareness of the event (see section 14.5).

In addition, the subjects will be instructed to immediately contact the investigator/investigation site in case of occurrence of any untoward event between visits and an unscheduled visit will be performed (see section 6.5.17). Throughout the entire investigation the investigator should also verify results of all assessments with respect to possible AEs.

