# 20.5 Assessment of Symptoms of Interest (SOIs)

### 20.5.1 Not Clinically Significant SOIs (examples)

Not clinically significant SOIs are those SOIs that cannot be verified e.g., through targeted subject questioning and/or examinations (also see section 14.2).

The below list is included as a guide and is not intended to be all inclusive:

- The subject is dissatisfied with treatment effect and reports SOI 'Face droop' because the lifting/volume effect did not turn out as desired,
- An anxious subject observes him/herself closely and reports an apparent feeling of 'Weakness or numbness in the arms or legs' but this cannot be verified in neurologic examination and subject confirms retrospectively that his/her mobility and sensitivity were not really restricted.
- The subject is unsure and selects an SOI by misinterpretation (e.g., 'difficulty speaking/speech impairment' although neither dysarthria nor aphasia occurred but he/she did not dare to speak normally to 'protect' the cheeks
- The SOI 'skin changing colour around eyes' corresponds to a local reaction that is already recorded in the diary as injection site reaction (e.g., 'bruising'),
- The SOI 'blurriness' is caused by a pre-existing underlying disease or treatment (e.g., due to dry eyes in a contact lens wearer).
- Technical failure(s). The subject ticked a SOI by mistake.

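### The on-site visit for neurological issues reported by phone is mandatory at only two of the four post-treatment calls, and diary entries of face droop, limb weakness or speech difficulty may be closed on questioning alone

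*Protocol*

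**What the plan says.** **Who gets F.A.S.T.** The Synopsis says that "A basic neurological examination (F.A.S.T) will be performed for all subjects who show signs of ophthalmic complications due to filler injection". Sections 4.4, 6.1.1 and 6.4.9 and Table 16 give the same condition. Footnote 17 of Tables 1 and 3 narrows it to "signs of ophthalmic complications due to filler injection in visual exams".

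**What the diary collects.** Section 6.4.19 lists face droop, weakness or numbness of the limbs, and difficulty speaking as symptoms of interest in their own right. Separately, all subjects must be asked about stroke signs (footnote 14 of Table 1, footnote 5 of Table 2, footnote 10 of Table 3).

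**How a diary symptom is checked.** Section 14.2 says it "must be verified by the investigator either by specific questioning of the subject and/or physical examination or visual inspection". Annex 20.5.1 describes symptoms that are not clinically significant as those that "cannot be verified e.g., through targeted subject questioning and/or examinations".

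**What the phone contacts require.** At Visit 2a, section 6.5.3 provides that for "neurological issues, or an unbearable injection site reaction an unscheduled on-site visit must be performed". Section 6.5.11 (Visit RT1a) says the same. Sections 6.5.5 (Visit 3a) and 6.5.13 (Visit RT2a) carry nearly the same sentence with *should* in place of *must*.

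**The concern.** A touch-up injects the same type of filler into the same area as the treatment before it, so the response to a neurological complaint the next day should be just as firm. As written, it is weaker after the touch-ups.

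The diary rule matters because of what follows from closing an entry. Under section 6.4.19, a symptom judged not clinically significant leaves a note in the source records and no adverse event entry. Several protective steps start only from an adverse event classification or a recognised event: 24-hour reporting (14.5.4), exclusion from touch-up and repeat-treatment (6.3.4.2, 6.3.5.2) and the stopping rule (16.1). There is no data monitoring committee (14.10). The decision to close therefore carries weight, and for the three symptoms that match the F, A and S items it may rest on a conversation.

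**Working it through.** No calculation applies; the check is a comparison of wording.

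**Step 1. The four scheduled calls.**

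| Call | Follows | Section | On-site visit for vision or neurological issues |
|---|---|---|---|
| 2a | baseline treatment | 6.5.3 | must |
| 3a | touch-up 1 | 6.5.5 | should |
| RT1a | repeat-treatment | 6.5.11 | must |
| RT2a | touch-up 2 | 6.5.13 | should |

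Two of the four are weaker, and both follow touch-ups.

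**Step 2. Other statements about the unscheduled visit.**

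- Section 4.4, on the call after each injection: *should*. It names adverse events and unbearable injection site reactions, not neurological issues.
- Section 6.5.17, to which all four calls refer: *may*, if the treating investigator judges it necessary.
- Section 6.4.19, for diary symptoms: *may*, if required.
- Section 14.2: subjects are told to make contact "in case of occurrence of any untoward event between visits and an unscheduled visit will be performed". This is the firmest wording, but it concerns contact started by the subject between visits, not expressly the scheduled call.
- Sections 6.5.6 and 6.5.14 (Visits 3b and RT2b): *should*. These are already on-site visits, so calling for an unscheduled on-site visit makes little sense there. The sentence appears to have been copied.

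**Step 3. Closing a diary entry.** Section 14.2 joins questioning to physical examination or visual inspection by *and/or*, so questioning alone satisfies it. Annex 20.5.1 uses the same construction and gives one example for each of the three symptoms:

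| Item | Diary symptom | How the example in 20.5.1 is closed | Examination named? |
|---|---|---|---|
| F | face droop | dissatisfaction, "because the lifting/volume effect did not turn out as desired" | no |
| A | limb weakness or numbness | "but this cannot be verified in neurologic examination and subject confirms retrospectively" that there was no real restriction | yes |
| S | speech difficulty | misinterpretation; dysarthria and aphasia said to be absent, without saying how this was established | no |

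One of three names an examination.

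**Step 4. Does the F.A.S.T. rule fill the gap?** No. Each statement of who receives F.A.S.T. requires ophthalmic signs, and the visit lists say only that it is done if applicable. A subject with an isolated diary entry of face droop does not meet the condition. By contrast, withdrawal from further treatment for neurologist-confirmed neurological symptoms (6.3.6) has no ophthalmic precondition.

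**The case against.** The case on the other side is substantial.

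- *The trigger is intended.* The log for Amendment 1 (19.1) records that F.A.S.T. was added after a regulator's comment, because ophthalmic complications are often accompanied by central nervous system complications. A reader might infer that the ophthalmic condition is a mistake. The documents do not support that. This stands, and the trigger should be kept.
- *Overt stroke signs already have a stronger route.* Section 6.4.9 requires emergency services and hospital transfer when stroke signs show, and referral to a neurologist. The diary tells subjects to seek immediate medical attention, and sites monitor entries between visits (6.4.19). A reader might infer that stroke signs without eye signs go unanswered. That is not so. But these rules act on signs that are recognised, or on the subject's own conduct. They do not make a site examine before closing an entry.
- *The examples in 20.5.1 are illustrative.* The annex calls its list a guide, and an example that is silent on examination does not forbid one. This stands. The point rests on the *and/or* in the two rules, not on the examples.
- *Must versus should looks like drafting drift.* Probably so, given the copied sentence in Visits 3b and RT2b. It is not evidence of a deliberate downgrade after touch-ups. A site following the text still meets the weaker word.
- *Section 4.4 is not the operative instruction.* It sits among pandemic measures and does not mention neurological issues. It needs aligning but is not the main evidence.
- *A later F.A.S.T. may be normal once a symptom has resolved.* True. It is a minimum before closure, not proof that the symptom was unimportant.

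**Conclusion.** The point holds as an inexpensive safety improvement. The text is firm at two of the four scheduled calls and softer at the other two without explanation, and it permits three stroke-type diary symptoms to be closed without examination.

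The practical size is small. Table 7 lists vascular occlusion, including stroke, as very rare. The safeguards in 6.4.9, 6.4.19 and 14.2 would catch most overt events. The protocol gives no basis for counting affected subjects, so none is offered. The Amendment 5 log suggests that recruitment was complete by then, in which case the change would bear mainly on the repeat-treatment phase; how much of that remains is not stated. A reader might look for consequences for the non-inferiority result. There are none, since neither rule affects the Week 24 responder assessment.

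The conclusion assumes that sites follow the wording as printed. Sites that already examine every such subject would see no change.

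**What to change.** 1. **Calls.** In 6.5.5 and 6.5.13, make the unscheduled on-site visit a *must* for vision changes or neurological issues. Align 4.4 and 6.5.17 by stating there that for these two the visit is mandatory. In 6.5.6 and 6.5.14, replace the copied sentence with an instruction to do the examination at that visit.
2. **F.A.S.T.** In 6.4.9 and footnote 17 of Tables 1 and 3, keep the present trigger and add subjects who report face droop, limb weakness or numbness, or speech difficulty. State that F.A.S.T. must not delay emergency transfer. Carry the addition to the Synopsis, 4.4, 6.1.1 and Table 16.
3. **Closure.** In 14.2 and 20.5.1, add that these three symptoms may be classed as not clinically significant only after a documented F.A.S.T., unless ticked by mistake.

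Cost: a protocol wording change, plus a few brief bedside examinations and unscheduled visits. F.A.S.T. is already a trial procedure. Sample size and analysis do not change.

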## Schedule of procedures and assessments

Table 1. Schedule of procedures and assessments for the initial treatment phase (Visit 1-to Visit 9 (SV1) (all subjects)

				Follow-up for initial treatment (baseline and touch-up treatment) (initial treatment phase)								
	Visit 1	Visit 2	Visit 2a	Visit 3	Visit 3a	Visit 3b	Visit 4	Visit 5	Visit 6	Visit 7	Visit 8	Visit 0
Visit	Screening 	Baseline 	Phone contact	TUP1	Phone contact 	Safety Follow-up 						(SV1) 
200	100		24 - 48	2 weeks	24 - 48	2 weeks	4 weeks	8 weeks	16 weeks	24 weeks	36 weeks	48 weeks
Day / week	Day-14 to	Day 0	hours after	after BL	hours after	after TUP1	after last	after last	after last	after last	after last	after last
	Day 0	^	Day 0	injection	Visit 3	injection	injection 	injection 	injection 	injection **	injection 	injection 
Visit window			±4 hours	± 3 days	±4 hours	±3 days	±5 days	±5 days	±/ days	±/ days	±/ days	±/ days
Procedure		r	1	u		r	1	F			r	
Informed consent	Χ*	10000000						.			e-	
Medical History 10	X	X*										
Aesthetic History	X	X*										
Prior and concomitant treatments 	x	X*	x	X	x	x	x	x	x	x	x	x
Demographics 	X*											
Fitzpatrick skin type	X*											
Body weight	X*						X	Х	Х	Х	Х	X
Urine pregnancy test 	X	X*		Χ*		X	X	X	X	Х	X	X
Visual examinations 		X 		X 11		X	X	Х	X	X	X	X
Neurological examinations 17		X		Х		Х	X	X	X	Х	X	Х
Clinical photography	X*25						X	X	X	Х	X	Х
MVDSS – blinded evaluator at site	X*4			X*			x	x	х	x	x	X4
MVDSS – central blinded photographic reviewer 	X						x	x	x	x	x	x
NLF-SRS –blinded evaluator at site 	X*			X*			x	X	x	x	X	х

			Follow-up for initial treatment (baseline and touch-up treatment) (initial treatment phase)									
	Visit 1	Visit 2	Visit 2a	Visit 3	Visit 3a	Visit 3b	Visit 4	Visit 5	Visit 6	Visit 7	Visit 8	
Visit	Screening 	Baseline 	Phone contact	TUP1	Phone contact 	Safety Follow-up 						(SV1) 
			24 - 48	2 weeks	24-48	2 weeks	4 weeks	8 weeks	16 weeks	24 weeks	36 weeks	48 weeks
Day / week	Day-14 to	Day 0	hours after	after BL	hours after	after TUP1	after last					
A MARKAGA AND A	Day 0	Duyo	Day 0	injection	Visit 3	injection	injection 					
Visit window			± 4 hours	±3 days	±4 hours	±3 days	±5 days	±5 days	±7 days	±7 days	±7 days	±7 days
Procedure	•										F	
Volumetric Change Measurements 	×						x	x	х	x	×	x
Assessment of eligibility	Х	X*	]	X*13								X 
Randomization		X*										
Treatment		X		X 16								
Modified GAIS  – blinded evaluator at site			÷.				X	х	Х	х	х	Х
Modified GAIS  - subject	rd.						X	Х	Х	Х	Х	Х
FACE-Q ™ "Satisfaction with Outcome" – subject 							х	х	х	х	х	x
FACE-Q ™ "Satisfaction with Cheeks" – subject 		Х*					X	X	х	Х	х	х
Evaluation of pain – subject (NPRS) 	14	X		X 								
Injection volume 		Х	10	X 								
Initiate / Explain subject diary 		X		X 								
Review subject diary 				Х		X	X					
Adverse events 14	X	X	Х	Х	Х	Х	X	X	Х	Х	X	X
Device deficiencies		X		X13								

*	Prior to injection (i.e., either at baseline or touch-up treatment (TUP1))
0	Screening and Baseline visits may be performed as one visit
1	Includes information on prior treatments, defined as all medications and non-drug therapies taken/received within the previous ten days prior to Screening up to end of study
2	Includes date of birth, sex, race and ethnicity
3	In women of childbearing potential only, including those who are postmenopausal for less than 12 months
4	Evaluation and grading of midface volume deficit by the blinded evaluator at the site (live assessment) using the 5-point MVDSS. The score does not have to be the same on both sides but must be 2 or 3.
5	Evaluation and grading of midface volume deficit severity by the central independent blinded photographic reviewer using the 5-point MVDSS and based on photographs
6	Evaluation of global aesthetic improvement using the modified GAIS against subject's photographs obtained at the Visit 1
7	Subject satisfaction will be determined using the FACE-Q ™ questionnaire "Satisfaction with Outcome"
8	Evaluation of subject appearance appraisal using the FACE-Q ™ questionnaire "Satisfaction with Cheeks"
9	NPRS starting immediately and every 15 min after last injection for 60 min post-treatment. Separate pain assessments will be performed for the right and left midface area treated.
10	Relevant medical history includes prior and ongoing concomitant diseases and possibly recurring conditions
11	Visual exams (including Snellen visual acuity, confrontational visual fields and ocular motility). The subject should wear the same corrective eyewear (i.e., glasses/contact lenses) at each assessment, if appropriate. At treatment visits: Examination will be performed both before and 30 min after the injection. For subjects not receiving TUP, exams will only be performed once.
12	Volumetric change measurement on photographs will be done centrally by the photography provider once the photography images are received at the photography provider after all subjects have finalized Visit 9 (SV1). The left and right midface will be evaluated separately.
13	Concerning only subjects who receive touch-up treatment
14	All subjects must be asked if they are experiencing or have experienced any signs/symptoms of vision changes or stroke since the injection or other events indicating an embolic event.
15	Repeat-treatment is optional and possible for all subjects who fulfill the eligibility criteria, irrespective of the treatment (either test device or comparator device) they received in the initial treatment (baseline plus touch-up). The subject does NOT have to return to his/her baseline severity to be permitted to receive a repeat-treatment, but the present condition of midface volume deficit has to meet the initial inclusion level of severity scores of 2 or 3 on the 5-point MVDSS (see section 6.3.5). The score does not have to be the same on both sides but must be 2 or 3. In case the subject is eligible in MVDSS score at Visit 9 (SV1), a full eligibility assessment for repeat-treatment will be performed (see Table 3).
16	Touch-up treatment for optimal correction if deemed necessary in the discretion of treating investigator
17	A basic neurological examination (F.A.S.T) will be performed for all subjects who show signs of ophthalmic complications due to filler injection in visual exams

18	Evaluation and grading of nasolabial folds severity by the blinded evaluator at the site (live assessment) using the 5-point NLF-SRS
19	Explain diary use incl. documentation of injection site reactions / symptoms of interest to the subject.
20	Review subject diary regarding injection site reactions / symptoms of interest; confirm review. Note: Subjects will record injection site reactions, and symptoms of interest (i.e., changes in vision or symptoms of stroke) over the first four weeks (28 days) after each treatment (i.e., 4 weeks after baseline treatment, and 6 weeks in case of touch-up treatment).
21	In case of Early Termination attempts should be made to perform the assessments described for Visit 9 (SV1).
22	Last injection always either refers to initial treatment (BL) or touch-up treatment (TUP1)
23	Injection volume will be documented by site of the midface (left/right) and for each of the 3 anatomical areas of midface treatment (anteromedial cheek, submalar, and zygomaticomalar)
24	Visit 9 (SV1) will be the end of study visit, in case an inclusion criterion is not met / an exclusion criterion is met for optional repeat-treatment (see section 6.3.5) and further follow up in screening is not useful because the subject will apparently not qualify for repeat-treatment.
25	In addition to clinical photography (3D photos), another baseline photo (2D) should be taken on-site at Visit 1.
Abbre Scale;	viations: MVDSS: Midface Volume Deficit Severity Scale; NLF-SRS: Nasolabial Folds Severity Rating Scale; GAIS: Global Aesthetic Improvement Scale; NPRS: Numerical Pain Rating SV: Screening Visit; TUP1: Touch-up treatment after baseline treatment

 Table 2. Schedule of procedures and assessments for screening phase for repeat-treatment (Visit SV2 to SV4)

	Screening phase for repeat-treatment			
Visit	Visit SV2  Visit SV3 		Visit SV4 	
VISIT	(optional)*	(optional)*	(optional)*	
Day / week	4 weeks after Visit 9 (SV1)	8 weeks after Visit 9 (SV1)	12 weeks after Visit 9 (SV1)	
Visit window	±7 days	±7 days	±7 days	
MVDSS  - blinded evaluator at site 	Х	X	X	
Concomitant treatments 	Х	X	Х	
Adverse events 	X	X	X	

*	Visits SV2 to SV4 are optional. As soon as the subject is eligible in MVDSS score, a full eligibility assessment for optional repeat-treatment will be done and Visit RT1 will be performed (see Table 3).		
1	Subjects do not have to return to their baseline severity of midface volume deficit to be eligible and receive a repeat-treatment, but the present condition of midface volume deficit has to meet the initial inclusion level of severity scores of 2 or 3 on the 5-point MVDSS (see section 6.3.5). The score does not have to be the same on both sides but must be 2 or 3.		
2	Midface volume deficit severity is determined by the blinded evaluator. Note: The blinded evaluator at the site is not blinded for treatment allocation during the repeat-treatment phase. However, he/she will be still blinded for the treatment a subject received during the initial treatment phase		
3	Visit SV4 will be the end of study visit for subjects who do not qualify for repeat-treatment. In case an inclusion criterion is not met / an exclusion criterion is met during the screening phase for repeat-treatment (see section 6.3.5) and further follow up in screening is not useful because the subject will apparently not qualify for repeat-treatment, SV 2 or SV 3 will be the end of study visit for the respective subject.		
4	All medications taken and non-pharmacological procedures applied by a subject during the course of a clinical study.		
5	All subjects must be asked if they are experiencing or have experienced any signs/symptoms of vision changes or stroke since the injection or other events indicating an embolic event.		
Abbreviations: MVDSS: Midface Volume Deficit Severity Scale; SV: Screening Visit; RT: Repeat Treatment			

Table 3. Schedule of procedures and assessments for repeat-treatment phase (Visits RT1 to RT5)

	Repeat-treatment and Follow-up for repeat-treatment (repeat-treatment phase)							
	Visit RT1 	Visit RT1a	Visit RT2	Visit RT2a 13	Visit RT2b 	Visit RT3	Visit RT4	Visit RT5
Visit		Phone contact	TUP2	Phone contact	Safety Follow-up			(EOS) 
Day / week	Up to 14 days after Screening Visit †	24 – 48 hours after RT1	2 weeks after RT1 injection	24 – 48 hours after RT2	2 weeks after TUP2 injection	4 weeks after last injection 	12 weeks after last injection 	24 weeks after last injection 
Visit window		± 4 hours	± 3 days	± 4 hours	±3 days	± 5 days	± 7 days	± 7 days
Procedure		-						
Assessment of eligibility	Х*		X*13					
Concomitant treatments 	Х*	Х	Х	Х	X	Х	Х	Х
Body weight	Х*		X			Х	Х	Х
Urine pregnancy test 	Х*		Χ*		Х	Х	Х	Х
Visual examinations 	Х		Х		X	Х	Х	Х
Neurological examinations 	Х		Х		Х	Х	Х	Х
MVDSS – blinded evaluator at site 	Х*		Χ*			Х	Х	Х
NLF-SRS – blinded evaluator at site 	Х*		X*			Х	Х	Х
Treatment	Х		X 16					
FACE-Q ™ "Satisfaction with Outcome" – subject 	X*		Х*			х	х	х
FACE-Q ™ "Satisfaction with Cheeks" – subject 	X*		X*			x	х	x
Evaluation of pain – subject (NPRS) 	Х		X 					
Injection volume 	Х		X 					
Initiate / Explain subject diary 	Х		X 					
Review subject diary 			x		X	Х		
Adverse events 10	X	X	X	Х	X	X	Х	X
Device deficiencies	Х		X 					

*	Prior to injection (i.e., either at repeat-treatment or touch-up treatment (TUP2))
+	Visit RT1 may be performed up to 14 days after Screening Visit case the subject qualifies for repeat-treatment at one of these Visits. Screening Visit are Visit 9 (SV1) to SV4.
0	Screening Visits (i.e., Visit 9 (SV1) to SV4) and Visit RT1 may be performed as one visit in case the subject qualifies for repeat-treatment at one of these visits. In case of only one visit, the following assessments do not need to be done twice
	- Visit 9 (SV1) = RT1: * pre-treatment assessments at Visit RT1
	- Visits SV2 to SV4 = RT1: MVDSS by blinded evaluator, concomitant treatments, adverse events
1	Defined as all medications and non-drug therapies taken/received within the previous ten days prior to initial Screening up to end of study
2	In women of childbearing potential only, including those who are postmenopausal for less than 12 months
3	Evaluation and grading of midface volume deficit by the blinded evaluator at the site (live assessment) using the 5-point MVDSS. Note: The blinded evaluator at the site is not blinded for treatment allocation during the repeat-treatment phase. However, he/she will be still blinded for the treatment a subject received during the initial treatment phase.
4	Evaluation and grading of nasolabial folds severity by the blinded evaluator at the site (live assessment) using the 5-point NLF-SRS.
6	Subject satisfaction will be determined using the FACE-Q ™ questionnaire "Satisfaction with Outcome"
7	Evaluation of subject appearance appraisal using the FACE-Q ™ questionnaire "Satisfaction with Cheeks"
8	Visual exams (including Snellen visual acuity, confrontational visual fields and ocular motility). The subject should wear the same corrective eyewear (i.e., glasses/contact lenses) at each assessment, if appropriate. At treatment visits: Examination will be performed both before and 30 min after the injection. For subjects not receiving TUP, exams will only be performed once.
9	NPRS starting immediately and every 15 min after last injection for 60 min post-treatment
10	All subjects must be asked if they are experiencing or have experienced any signs/symptoms of vision changes or stroke since the injection or other events indicating an embolic event.
13	Concerning only subjects who receive touch-up treatment.
16	Touch-up treatment for optimal correction if deemed necessary in the discretion of treating investigator
17	A basic neurological examination (F.A.S.T) will be performed for all subjects who show signs of ophthalmic complications due to filler injection in visual exams
19	Explain diary use incl. documentation of injection site reactions / symptoms of interest to the subject.
20	Review subject diary regarding injection site reactions / symptoms of interest; confirm review. Note: Subjects will record injection site reactions, and symptoms of interest (i.e., changes in vision or symptoms of stroke) over the first four weeks (28 days) after each treatment (i.e., 4 weeks after repeat-treatment, and 6 weeks in case of touch-up treatment.
21	In case of Early Termination attempts should be made to perform the assessments described for Visit RT5.
22	Last injection in repeat treatment phase always either refers to repeat-treatment (RT1) or touch-up treatment (TUP2)

23 Injection volume will be documented by site of the midface (left/right) and for each of the 3 anatomical areas of midface treatment (anteromedial cheek, submalar, and zygomaticomalar)

Abbreviations: MVDSS: Midface Volume Deficit Severity Scale; NLF-SRS: Nasolabial Folds Severity Rating Scale; GAIS: Global Aesthetic Improvement Scale, NPRS: Numerical Pain Rating Scale; SV: Screening Visit; RT: Repeat Treatment; TUP2: Touch-up treatment after repeat-treatment

